RIOT	return to intended oncological treatment
TC	Total Cardiology

PROTOCOL SYNOPSIS

TITLE	Trimodal prehabilitation for cystectomy patients to enhance post-operative care: A randomized control trial
VERSION	1.0
STUDY DESIGN	Pragmatic RCT with assessor blinding
STUDY	52 weeks
STUDY CENTRES	Single Centre Trial (Rockyview General Hospital, Calgary, AB)
PRIMARY OBJECTIVE	To investigate the effects of a trimodal 8-week prehabilitation program on the return to function of patients undergoing RC as measured by six-minute walk test (6MWT) and walking speed, as well as on traditional clinical outcome measures including length of hospital stay, rates of morbidity, and return to oncological treatment.
SECONDARY OBJECTIVES	
To investigate the impact and patient acceptability of a trimodal 8-week prehabilitation program on patient satisfaction and quality of life, as determined through questionnaires, and patient interviews
 
To investigate the effects of a trimodal 8-week program on traditional outcomes including length of hospital stay, rates of morbidity, and return to oncological treatment
 
To establish appropriate criteria that effectively identifies and triages those patients who would benefit most from prehabilitation
 
To evaluate which functional outcome measures represent a valid index of recovery and are sensitive to change.

NUMBER OF PARTICIPANTS	50
DIAGNOSIS AND MAIN INCLUSION CRITERIA	
Inclusion Criteria:
 
 1. Male or female ≥ 18 years of age at time of consent for surgery. 2. Documentation of bladder cancer diagnosis as evidenced by diagnostic imaging and biopsy. 3. May or may not receive adjuvant therapy. 4. Written informed consent obtained from subject 
Exclusion Criteria:
 
 1. Presence of a condition or abnormality that in the opinion of the

	
investigator would compromise the safety of the patient or adherence to the program. This includes:
 
 a. American Society of Anesthesiologists (ASA) health class status 4-5; b. Co-morbid medical, physical, and/or mental conditions including dementia, disabling orthopedic and neuromuscular disease, psychosis; c. Severe cardiac abnormalities, end-stage organ disease, sepsis, or morbid obesity (BMI greater than 35); 
 2. Undergoing radical cystectomy for a reason other than bladder cancer. 3. Poor comprehension of English or French 4. Screened by Total Cardiology staff and determined to be inappropriate for prehabilitation at their facility.
INTERVENTION / CONTROL GROUP	
Control: Radical cystectomy. Enhanced Recovery Protocol will be followed. Home exercise program & nutritional information provided.
 
Intervention: Trimodal prehabilitation received prior to radical cystectomy. Enhanced Recovery Protocol will be followed.

DURATION OF PARTICIPATION	16 weeks
EVALUATIONS	5 evaluation visits and 8 individual interviews conducted by a PaCER trained researcher.
STATISTICS Primary Analysis Plan	An available case analysis without imputation of missing values will be conducted. All analyses will be performed using Stata 14.1 (2015, StataCorp). All continuous variables will be reported as mean, 95% confidence interval. Categorical variables will be presented as frequency (%) and compared using Pearson's χ^2 test. A mixed effects model will be used to analyze repeated measures, including our primary outcome the 6MWT. A P-value <0.05 will be considered statistically significant.
Rationale for Number of Subjects	Funding is limited to \$15,000. This allows for a study of ~25 prehabilitation participants and 25 participants undergoing standard-of-care treatment.

1 INTRODUCTION

1.1 Abstract

A trimodal preoperative intervention known as prehabilitation (involving exercise, nutrition and psychological care) has been found to successfully improve functional recovery, an important patient-centered outcome, in colorectal surgery patients following the Enhanced Recovery After Surgery (ERAS) pathway. It is unknown whether the same program will be effective in patients undergoing surgery for bladder cancer (cystectomy). It is an opportune time to study prehabilitation at the Rockyview General Hospital given the recent roll-out of the Enhanced Recovery Protocol (ERP) for cystectomy patients and ongoing implementation of an integrated prehabilitation program.

Objective: To evaluate the appropriateness of a standardized prehabilitation program for implementation into an ERP for cystectomy patients and determine whether prehabilitation facilitates earlier recovery of functional capacity, as measured by six-minute walk test (6MWT)

Hypothesis: Prehabilitation will ultimately improve recovery of functional capacity, clinical and patient-centered outcomes in patients undergoing radical cystectomy for bladder cancer.

Design: A pragmatic randomized control trial of radical cystectomy patients following ERP and an 8-week trimodal prehabilitation program consisting of exercise therapy combined with nutritional counselling, protein supplementation, and psychological care will be compared to a cohort of patients following ERP care alone.

Main Outcome Measures: Return to preoperative functional walking capacity, as assessed using the validated six-minute walk test at the 8th postoperative week. All measures will be recorded at baseline, the day of surgery, and four and eight weeks after surgery. Traditional clinical outcome measures (e.g., length of hospital stay) will also be evaluated. Finally, patient interviews will be conducted to evaluate the appropriateness of prehabilitation.

Conclusion: The proposal will provide insight into the feasibility and effectiveness of trimodal prehabilitation for radical cystectomy patients and ultimately lead to improved clinical outcomes and reduced morbidity.

1.2 Background

In 2017 an estimated 8,900 Canadians will be diagnosed with bladder cancer¹. The mainstay of surgical treatment for muscle-invasive bladder cancer is radical cystectomy (RC) with lymph node dissection. Large prospective cohort studies suggest that at least 64% of patients undergoing RC experience at least one complication within 3 months^{2,3}. In an attempt to reduce

these complications and shorten length of hospital stay postoperatively, Rockyview General Hospital (RGH) is implementing a new enhanced recovery protocol (ERP) that will employ multidisciplinary, evidence-based clinical interventions, drawing upon the Enhanced Recovery After Surgery (ERAS) protocols⁴ for its development. ERAS protocols have been shown to reduce length of hospital stay and morbidity post-colorectal surgery, and provide an evidence-based, multidisciplinary approach to surgical care. It is unclear whether available evidence suggests ERPs facilitate earlier recovery of strength and function, and previous efforts to improve recovery have traditionally focused on the postoperative period, during which cancer patients may be fatigued, concerned about disturbing the healing process, or anxious as they await additional treatments for their underlying condition.⁵ Given this, the preoperative period may in fact be a more salient time to intervene. Optimizing an individual's functional capacity can begin during the waiting period before surgery as it capitalizes on the better physical health compared with the acute postoperative period^{6,7}. Moreover, interventions prior to surgery can potentially improve complication rates perioperatively. This process of enhancing an individual's functional capacity to withstand the stress of surgery is called prehabilitation⁸.

Randomized controlled trials (RCTs) have demonstrated that a comprehensive trimodal prehabilitation program, a program consisting of exercise therapy, nutritional counseling with protein supplementation, and psychological care before surgery, improved the functional exercise status of colorectal surgery patients⁹. In fact, twice as many prehabilitated patients¹⁰ had returned to their pre-surgery walking capacity by the eighth postoperative week compared to traditional care⁵. A case study of a frail, elderly cystectomy patient reveals similar improvements¹¹ and a recently published RCT concludes that a dedicated 2-week exercise program for patients undergoing RC can improve muscle power and allow for earlier return to preoperative function¹². These results suggest that establishing a prehabilitation program for patients undergoing RC may also provide benefits. Indeed, RC patients may attain a greater benefit from prehabilitation since the rate of complications post-cystectomy is more than double that reported for colectomy¹³.

2 STUDY RATIONALE

Recent research⁶⁻¹³ demonstrates that many side effects associated with surgical stress can be attenuated utilizing well designed interventions. In view of the impact of cancer on physical, nutritional and psychological status, it is necessary to optimize body reserves preoperatively to prepare the patient for the stress of surgery. This study will provide guidance to clinicians for optimizing RC patients preoperatively and will contribute to our understanding of which outcome measures represent a valid index of recovery and are sensitive to changes. Additionally, RGH has recently implemented an ERP for patients undergoing RC which includes the option for an 8-week prehabilitation program hosted in the community through Total Cardiology (TC). Total Cardiology is a private cardiology practice in Calgary with a dedicated multi-disciplinary

team of health care practitioners including cardiologists, kinesiologists, and registered dietitians. Their scope-of-practice includes guided exercise programs specifically for patients undergoing cardiac rehabilitation and they are well versed with exercise stress testing. Given this opportunity, it is an optimal time to study the effects of such a program, the results for which can be directly applied to the improvement and refinement of the current prehabilitation program.

The results of this pilot randomized study will form the basis for potential multi-site studies and will assist with obtaining additional funding. In addition, the organizational and logistical details established here in, provide a framework for which future surgical prehabilitation programs can be based, with an aim of optimizing the preoperative period and minimizing morbidity.

2.1 Risk / Benefit Analysis

2.1.1 Risk Assessment

Risks associated with an exercise program include minor aches and pains, potential for mechanical injuries, such as strains & sprains, and cardiovascular problems, such as heart arrhythmias, heart attack, or sudden cardiac arrest¹⁴. Participants undergo a medical evaluation by the Total Cardiology team to ensure participants are sufficiently healthy and medically stable to participate in a program. By tailoring the exercise programs to the individual needs of each participant, risks for mechanical injuries and exercise-associated complications are sought to be minimized. Participants are encouraged to take rests and keep physical activity within a moderate range to ensure safe participation in the program.

Typical risks associated with the use of oral nutrition supplements are rare, but include constipation, diarrhea, nausea and vomiting. Participants will undergo evaluation by a Registered Dietitian and will be monitored for adverse effects throughout the program. Pre-existing medical conditions such as diabetes may impact the ability to use nutritional supplements. These conditions will be reviewed by the Registered Dietitian and an appropriate personalized nutrition care plan will be developed in conjunction with the participant.

With respect to interviews, sharing personal experiences of surgery might make some patients uncomfortable. Participants will be advised to share only what they are comfortable with sharing. Participants will be informed that if at any time they experience feelings of anxiousness, sadness, or discomfort, they have the right to take a break during the interview, postpone the interview, or withdraw their consent to participate.

2.1.2 Benefit Assessment

Generally speaking, the benefits associated with exercise and good nutritional intake, far outweigh the risks. Exercise has been linked to improving the status of many physical and mental conditions including cardiovascular disease, mental health, obesity, diabetes, and chronic pain and has been shown to improve cardiovascular function by optimizing the ventilation/perfusion

of the lungs and improving the cardiac output of the heart¹⁵. As the purpose of this study is to observe how side effects associated with surgical stress may be attenuated, the benefits of these interventions will become clearer. Given the large number of positive effects of exercise and good nutrition, it is hoped these initiatives will facilitate the recovery process and reduce impact to a person's functional status, thereby improving quality of life.

In view of the impact of cancer on physical, nutritional and psychological status, it is necessary to optimize body reserves preoperatively to prepare the patient for the stress of surgery. This study could provide some direction to guide clinicians in optimizing the perioperative period in patients undergoing bladder surgery as well as contributing to our understanding of which outcome measures represent a valid index of recovery and are sensitive to changes.

Finally, by conducting individual interviews, participants will have a direct impact on how prehabilitation is carried out in the future. They will have the opportunity to shape the program and ensure it is in accordance with their capabilities and beliefs. It should also be mentioned that this study has the potential to affect organizational change within Alberta Health Services by providing the groundwork research for which future health care management decisions can be made in an evidence-based manner.

This said, it is not immediately clear that prehabilitation will lead to the proposed functional benefits and our team is acutely aware of additional costs associated with such a program (i.e. facility & protein supplement costs). Benefits for participants are best contrasted with a control group following the standard of care and a basic home exercise program and can allow for better decision making from an organizational level.

3 STUDY OBJECTIVES

3.1 Research Question

Does an 8-week trimodal prehabilitation program consisting of exercise therapy combined with nutritional counseling, protein supplementation, and psychological care of patients undergoing radical cystectomy improve postoperative functional and quality of life (QOL) outcomes compared to patients who follow ERP care alone?

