4 STUDY DESIGN

4.1 Study Overview

This is a single center, single-blind, pragmatic randomized-control trial. There will be a total of 50 (fifty) participants in the study. Each participant will be randomly enrolled into a prehabilitation or no-prehabilitation group at time of consent for RC and those in the intervention group will undergo 8 weeks of prehabilitation through the Total Cardiology program, hosted through the Repsol Centre. Each participant, independent of study group assignment, will receive the standard treatment as outlined in the Enhanced Recovery Protocol (ERP) for Radical Cystectomies (see Appendix 1). Those enrolled in the prehabilitation group will attend 2 supervised exercise-based sessions per week and will complete a home-exercise program three times per week (total 5 exercise sessions per week). In addition, they will receive 5 protein supplement drinks per week to consume after exercise, and will attend classes on nutrition and stress/anxiety reduction techniques. Measurements will be taken at baseline, 6 weeks (as a part of their regularly scheduled pre-admission clinic appointment), 8 weeks (just prior to surgery), 4 weeks post-op, and 8 weeks post-op.

Those patients enrolled in the no-prehabilitation group will receive a general, unsupervised, home-exercise program, information regarding good nutrition. They will be followed at their regularly scheduled appointments. Again, measurements will be taken at the same time intervals as the prehabilitation group.

Screening data will be reviewed to determine subject eligibility. Subjects who meet all inclusion criteria and none of the exclusion criteria will be entered into the study.

The following treatment groups will be established:

- Standard ERP + Trimodal Prehabilitation
- Standard ERP

Total duration of subject participation will be approximately sixteen weeks. Total duration of the study is expected to be approximately 1.5 years.

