5.2 Components of Trimodal Prehabilitation

5.2.1 Exercise Program

The exercise component will consist of approximately two 60 min sessions of supervised resistance and aerobic exercises. The sessions will be under the supervision of a kinesiologist and will take place in collaboration with the Total Cardiology group out of the Repsol Sport Centre. Each participant's program will be individualized based upon the baseline fitness test and will include:

- 5 min warm-up,
- 25 min of aerobic exercise (starting at 30-40% of heart rate reserve (HRR) and progressing to 50-60% HRR as tolerated by participant),
- 25 min of resistance training (6 exercises targeting major muscle groups performed at moderate intensity), and
- 5-10 min cool-down and stretching period.
- Clear explanations & demonstrations of program by the kinesiologist

In addition, patients will be asked to carry out a 60min aerobic-based exercise program at home (i.e. walking), unsupervised, 3 days/week, and complete incentive spirometry breathing exercises 3 times/day for 10 breaths. Incentive spirometry has been shown to have beneficial effects on post-operative outcomes¹⁹ and will be included for this reason. Participants will record these additional activities in a journal that is provided to them at the start of their program.

Training intensity progression will be advised by the kinesiologist when the participant can complete aerobic exercise with mild exertion and/or when the participant can complete 15 repetitions of a given resistance exercise.

The kinesiologist will follow all participants to assess program adherence (including unsupervised sessions documented in patient's journal) and to address any barriers that may prevent ongoing participation.

The control group will receive the regular radical cystectomy information and will be asked to complete a 60min aerobic-based home exercise program, unsupervised, 5 days/week, along with incentive spirometry breathing exercises 3 times/day for 10 breaths. This group will also record their activities in a journal and a member of the research team will check in by telephone weekly to assess adherence and address any barriers or questions the patient may have.

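### The abstract and research question name the comparator as ERP care alone, but controls are also prescribed a supported preoperative home exercise program

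*Protocol*

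**What the plan says.** Two places define the comparison as prehabilitation against the enhanced recovery protocol (ERP) with nothing added. The research question in Protocol section 3.1 reads "compared to patients who follow ERP care alone". The Design paragraph of section 1.1 says that the prehabilitation patients "will be compared to a cohort of patients following ERP care alone".

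Five places give controls something more:

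- **Synopsis, Intervention / Control Group:** "Home exercise program & nutritional information provided".
- **Section 2.1.2:** benefits are "best contrasted with a control group following the standard of care and a basic home exercise program".
- **Section 4.1, narrative:** controls "will receive a general, unsupervised, home-exercise program, information regarding good nutrition".
- **Section 5.2.1:** besides the usual surgical information, controls are prescribed the following: "60min aerobic-based home exercise program, unsupervised, 5 days/week, along with incentive spirometry breathing exercises 3 times/day for 10 breaths". Controls also keep an activity journal, and "a member of the research team will check in by telephone weekly to assess adherence and address any barriers".
- **Section 7.1, Visit 1 item 10:** the home program and nutrition information are handed over at baseline, directly after randomization.

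The arm label in section 4.1 (standard ERP) and the arm description in section 5.1.1 do not mention the home program. Both are incomplete, but they do not deny it.

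**The concern.** The research question fixes which contrast the result will be read against. If controls have been asked to exercise five days a week before surgery and are telephoned weekly about adherence, the randomized comparison is between two preoperative exercise strategies on top of ERP. Comparing prehabilitation with ERP and no added exercise is a different question.

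This affects how the result can be used. Section 2.1.2 wants the trial to inform organizational decisions in view of the facility and supplement costs. Section 2 wants it to be the basis for multi-site studies and further funding. An estimate and confidence interval reported as the answer to 3.1 would be attached to an alternative that no participant was randomized to. A null or small difference could then be read as prehabilitation adding nothing to ERP, which this comparison cannot show.

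**Working it through.** The protocol gives no figure to reproduce here. It states no effect size, standard deviation or power, and sections 4.5 and 9.2 rest the sample size on funding. The check is to add up what each arm is prescribed and then to ask whether the control program could simply be part of the ERP.

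**Step 1. Prescribed exercise per week (section 5.2.1).**

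- Control: 5 sessions × 60 min = 300 min.
- One supervised prehabilitation session: 5 (warm-up) + 25 (aerobic) + 25 (resistance) + 5 to 10 (cool-down) = 60 to 65 min.
- Prehabilitation: 2 × (60 to 65) + 3 × 60 = 300 to 310 min, in 2 + 3 = 5 sessions. Section 4.1 confirms the total of five.
- Incentive spirometry: three times a day for 10 breaths in both arms.

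The arms do not differ in being prescribed preoperative exercise, in sessions per week or, to within 10 minutes, in weekly time.

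**Step 2. What does differ.** Only the prehabilitation arm has:

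- supervision by a kinesiologist;
- individualization from a baseline fitness test;
- aerobic work progressed towards 50-60% of heart rate reserve;
- resistance training, 2 × 25 = 50 min/week;
- protein supplements and nutrition classes;
- a dietitian on hand at supervised sessions;
- the anxiety-reduction class.

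These components, over and above a supported home program, are what the trial compares.

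**Step 3. Is the control program preoperative?** Yes. It is issued at Visit 1. Visit 2, at the pre-admission clinic two weeks before surgery (section 6.3), reinforces the home program. Visit 3, on the day of surgery, reviews the diary for compliance. Controls keep a journal too, so the natural reading is baseline to surgery.

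**Step 4. Is it part of the ERP?** The visible text points the other way:

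- Section 2.1.2 names the standard of care and the home program as two things.
- Section 5.2.1 lists the regular cystectomy information first and the program after it.
- Section 5.1.1, describing ERP care, mentions only instruction on postoperative exercises.
- The weekly calls come from the research team.

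The term ERP does not settle the matter alone, because section 2 says that the hospital's ERP itself includes an optional eight-week prehabilitation program.

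**Step 5. Compare with 3.1.** The question names ERP alone. The trial randomizes to ERP plus a supported home program. These coincide only if the home program has no effect on the outcomes, which the protocol does not claim.

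**The case against.** The strongest reply is that this is shorthand in an abstract and in a one-sentence question. The control arm is described in five operative places, with a rationale in 2.1.2, and the primary objective in 3.2 names no comparator. Nobody running the trial would treat controls differently because of 1.1 or 3.1, and harm arises only if the authors report against their own arm definitions. This stands as a limit on severity. It does not remove the point, because the research question is the statement that the conclusion is meant to answer.

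Appendix 1, which sets out the ERP, is not shown. Some overlap between the home program and ERP content cannot be excluded, so the reading in step 4 is an inference from 2.1.2, 5.1.1 and 5.2.1. This also stands.

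Equal minutes are not equal training. No intensity is stated for controls, adherence is unknown, and only one arm does resistance work. That is correct, and the tally shows only that both arms are prescribed preoperative exercise.

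A reader might go further in three ways that the documents do not support:

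- **That the active control is a flaw or is concealed.** It is disclosed repeatedly and justified in 2.1.2.
- **That the loss of effect or power can be quantified.** The protocol gives no effect size and no information on how much benefit the home program delivers. Any such figure would be an assumption and not a measure of this plan.
- **That the control program's duration is undefined or shorter than eight weeks.** The Visit 1 to Visit 3 procedures indicate that it runs from baseline to surgery.

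**Conclusion.** The point holds as an inconsistency between the stated question and the arms that are randomized. Sections 1.1 and 3.1 name a comparator that the synopsis, 2.1.2, 4.1, 5.2.1 and Visit 1 do not deliver. Both arms are prescribed five sessions and about 300 minutes of exercise a week (300 against 300 to 310), so the estimate concerns supervised trimodal prehabilitation against a supported home program.

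The consequence is asymmetric. A null or small difference would not answer 3.1 as worded. With about 50 participants it would not prove lack of benefit against any comparator in any case. A positive difference would still support benefit over ERP alone, provided that the home program does no harm.

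Severity is minor to moderate. The mismatch in wording is certain. That the program is additional to the ERP is well supported by the visible text but depends on Appendix 1.

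**What to change.** Keep the design. In section 1.1 (Design) and section 3.1, replace ERP care alone with: *ERP plus the unsupervised home exercise program and nutrition information described in section 5.2.1 and Visit 1*. Add a sentence stating that conclusions are limited to that contrast. Cross-reference section 5.2.1 in the section 4.1 arm label and in section 5.1.1.

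Referring to the operative sections is safer than writing a new list of control components. Sections 4.6 (step 6) and 6.6 do not restrict dietitian assessment to one arm, so a fresh list could leave something out. The synopsis, 2.1.2, the 4.1 narrative and Visit 1 need no change.

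The cost is a few lines of rewording, with no effect on procedures, visits or sample size. The downside is a narrower stated claim, with no direct estimate against ERP alone.
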